#### **Statistical Considerations**

Data Analysis. All quantitative analyses will be conducted using SAS v.9.4 (SAS Institute Inc., North Carolina, USA). Oualitative interview data will be transcribed and sorted into thematic categories using constant comparison within the framework of grounded theory. We will use linear regression to model the change in infant intake and maternal responsiveness (Aim 1) and change in WLZ, skinfolds, waist circumference (Aim 2) by the primary study variable of *clear* versus *opaque* group. For Aim 3, we will examine the feasibility, fidelity, adherence, acceptability, and safety of the intervention by summarizing quantitative and qualitative data related to recruitment and retention, mothers' use of their assigned bottles, perceptions of and barriers to using the bottles, and any issues related to infant inadequate weight gain or weight loss. We will then explore whether variations in intervention feasibility, fidelity, adherence, acceptability or safety are correlated with baseline characteristics of mothers (e.g., weight status, race/ethnicity, socioeconomic status, parity, feeding practices and styles, non-maternal caregiver involvement in feeding) and infants (e.g., sex, birth weight, weight status, temperament). Finally, we will assess whether the effects of the intervention on infant intake, maternal responsiveness, and infant WLZ change are moderated by the following factors: nipple type; mothers' adherence to the intervention, race/ethnicity, parity, or feeding practices and styles; infants' sex, temperament, and timing of solid food introduction; and the extent to which non-maternal caregivers are feeding the infant. Moderation will be explored by including a group by moderator interaction term in the linear regression models used to explore Aims 1 and 2. All inferential analyses will be preceded by appropriate descriptive statistics and graphs to determine that assumptions for linear regression are satisfied.

**Power calculations.** The proposed sample size (n=100) was selected so that there will be adequate power to test for statistical significance for study aims. Because our previous research has shown <10% attrition after 12 weeks, we conservatively estimate 20% of participants will drop out and 120 mother-infant dyads will be recruited to account for this predicted attrition rate. For Aim 1, which examines the impact of bottle type on infant intake and maternal responsiveness, there is 80% power to detect a 19.1 mL difference in intake and 1.32 point difference in change of NCAFS score from baseline to 12-week follow-up between the *clear* and *opaque* groups, using  $\alpha = .05$ . For Aim 2, which examines the impact of bottle type on weight for length z-scores (WLZ), there is 80% power ( $\alpha = .05$ ) to detect a difference of 0.59 in change of WLZ from baseline to 12-week follow-up between the *clear* and *opaque* groups. Given rapid weight gain has been defined as z-score change  $\geq 0.67$  SD, a between-group difference in WLZ change of this magnitude (0.59 SD) would be clinically significant. Power calculations are based on a pilot study for which the between-subject standard deviation for infant intake was 33.7 mL and for the NCAFS scales is 1.91; this calculation also assumes that the mothers assigned to the *clear* group will have a higher correlation in scores between baseline and 12-week follow-up (r = .55), whereas mothers assigned to the *opaque* group will have a lower correlation in scores between baseline and 12-week follow-up (r =.40). The latter calculation assumes the standard deviation for WLZ is 1.0, and that the correlation between WLZs over 12-weeks for infants is  $r = .45^{.60}$ 

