#### **Assessments and Measures**

As illustrated in the **Table**, we will conduct two assessments (separated by one day) at both study entry and completion to objectively measure infant intake and maternal responsiveness. Two brief visits will occur at weeks 2 and 6 to assess infant growth and maternal adherence to the intervention. All assessments will be administered by blinded research assistants.

Study Week:	1	1	2	6	12	12
Assessment Type:	Pre- Test 1*	Pre-Test 2*	Brief visit for	Brief visit for	Post-Test 1*	Post- Test 2*
Bottle used during observation: Clear Bottle Group	Clear	Opaque	growth check	check	Opaque	Clear
Opaque Bottle Group	Opaque	Clear			Clear	Opaque

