### Table. Example Assessment Timeline and Type of Bottles Used during Feeding Observations

\*Home-based assessments within the same week will be separated by one day; conditions will be counterbalanced.

Home-Based Assessments. Two research assistants will visit the mother's home in the morning (to control for infants' circadian rhythms and variations in intake) and will arrive approximately one hour prior to a time when an infant typically takes a bottlefeeding. Mothers will be asked to hide all bottles prior to each visit to ensure research assistants remain blinded. We will call the mother the evening before each visit to assess whether any disruptive events that may negatively influence the infant's behavior (e.g., colds, teething) occurred; if a disruptive event is reported during this phone call, the visit will be rescheduled. After a short acclimation period, we will interview the mother about when the infant last fed and slept and will conduct additional assessments. When the mother and infant are ready to feed, we will set-up two video cameras (GoPro Hero 4, California, USA) at two different angles (to obtain clear views of both the mother and the infant) ~10 feet in front of a location where the mother typically bottle-feeds her infant and will record the mother feeding her infant using clear or opaque bottles. The mother will be instructed to feed her infant as she normally would at home and the research assistants will wait in another room to minimize any possible influence on the mother's or infant's feeding behaviors. Additional questionnaires will be completed after feeding.

**Measures.** We will evaluate our intervention along multiple dimensions to fully understand the impact of opaque bottles on feeding outcomes and the feasibility of scaling this intervention for larger trials.

- **Infant intake** will be assessed by weighing the infant's bottle before and after each feeding observation using a top-loading balance (SP601 Scout Pro Portable Balance, Ohaus, New Jersey, USA). We will also note the type of nipple used and will control for nipple flow rate in all analyses.

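### Aim 1 does not name which of the four filmed feeds form the change score, and two natural readings cancel all or part of an immediate bottle effect

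*Combined protocol and SAP*

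**What the plan says.** Under Assessments and Measures, "we will conduct two assessments (separated by one day) at both study entry and completion to objectively measure infant intake and maternal responsiveness". The accompanying Table, titled "Example Assessment Timeline and Type of Bottles Used during Feeding Observations", has one row per arm for the bottle used. Each arm has one clear-bottle and one opaque-bottle feed at entry, and the same again at week 12. The footnote adds: "Home-based assessments within the same week will be separated by one day; conditions will be counterbalanced". The Randomization paragraph places disclosure of the group to the mother at the end of the second entry visit, so both entry feeds come before she knows her group.

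The Data Analysis paragraph of Statistical Considerations states: "We will use linear regression to model the change in infant intake and maternal responsiveness (Aim 1"), with clear versus opaque group as the main explanatory variable. The Measures section adds one covariate for every analysis: "We will also note the type of nipple used and will control for nipple flow rate in all analyses".

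The power paragraph describes the aim as follows: "For Aim 1, which examines the impact of bottle type on infant intake and maternal responsiveness". It uses one between-subject SD and one baseline-to-week-12 correlation per arm, as if there were one score per time point. No section says which feed is the baseline score, which is the week-12 score, whether the two are averaged, or whether the bottle used in a feed enters the model.

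**The concern.** The study's rationale is an effect within the same feed: the Statement of Purpose reports 26% lower intake with opaque, weighted bottles in the earlier laboratory trial. Such an effect would already be present in the opaque-bottle entry feed of both arms. Whether it survives in the Aim 1 contrast therefore depends on which feeds are subtracted from which.

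Aim 1 hypothesises that mothers using opaque bottles over 12 weeks will feed less and respond more to cues. If the change is built in a way that removes the immediate effect, the test addresses only what was learned beyond it. A null could then be read as evidence against the bottle when the analysis was not able to see the effect that motivated the trial.

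**Working it through.** **Inputs.** From the power paragraph: SD 33.7 mL, r = .55 (clear arm) and .40 (opaque arm), detectable difference 19.1 mL, alpha .05, n = 100. Assumed: 50 per arm, two-sided test. Not in the documents, so varied: the correlation between two feeds in the same week, and G, the ratio of week-12 to entry mean intake from the clear bottle. The 19.1 mL is used as an illustrative week-12 effect, not an expected one.

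**The plan's own figure.** Change variance per arm is 2 × SD² × (1 − r), that is 0.90 SD² (clear) and 1.20 SD² (opaque). SE = √(33.7² × 2.10 / 50) = 6.91 mL. The detectable difference at 80% power is 19.35 mL (normal) or 19.54 mL (t), and power at 19.1 mL is 78%. A single-time comparison with the raw SD gives 19.07 mL. The figure is therefore reproduced closely either way and does not reveal which feeds were meant.

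**What each reading estimates.** Let m0 and m12 be the clear-bottle means at entry and week 12, and b0 and b12 the immediate opaque-minus-clear effects, equal in both arms. The contrast is opaque arm minus clear arm.

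- Average of both bottles: each arm changes by (m12 + b12/2) − (m0 + b0/2). The contrast is 0, whether the effect is constant or proportional.
- Assigned bottle at both times: [(m12 + b12) − (m0 + b0)] − [m12 − m0] = b12 − b0. This is 0 if the effect is constant in mL. If it is proportional, b0 = b12/G, so the contrast is b12 × (1 − 1/G).
- Clear-bottle baseline to week-12 assigned bottle: [(m12 + b12) − m0] − [m12 − m0] = b12, the full effect.

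**Size, constant immediate effect of 19.1 mL** (simulated; closed forms shown where simple).

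| Aim 1 contrast | Expected difference | Rejection rate |
|---|---|---|
| Averaged change | 0 mL | 5% |
| Assigned-bottle change | 0 mL | 5-6% |
| Clear baseline to week-12 assigned bottle | about −19.1 mL | 78% |
| Week-12 assigned bottle, adjusted for clear baseline | −19.1 mL | 89% |
| Week-12 assigned bottle, adjusted for both baselines | −19.1 mL | 92% |

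Check of the last two rows. With one baseline the residual variances are 1 − .55² = 0.6975 and 1 − .40² = 0.84, so SE = √(33.7² × 1.5375 / 50) = 5.91 mL. With two baselines and same-week correlation equal to r, the explained share is 2r²/(1 + r), so SE = √(33.7² × 1.381 / 50) = 5.60 mL. At a same-week correlation of .85 the two-baseline SE is √(33.7² × 1.50 / 50) = 5.84 mL, and power is still about 90%.

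**Size, proportional immediate effect.** At assumed G = 1.25, 1.5 and 2 the assigned-bottle change keeps 19.1 × (1 − 1/G) = 3.8, 6.4 and 9.6 mL. Power is about 9%, 15% and 28%. The averaged change stays at 0 mL.

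**If some or all of the effect is learned.** Averaged-score power depends on the unknown same-week correlation. The range runs from the 12-week values (.55 and .40) up to .85.

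- Learned effect on both bottles: averaged change 97% down to about 84%; adjusted averaged score 99% down to about 92%; assigned-bottle change 78%.
- Half immediate, half learned: averaged change 49% down to about 31%; assigned-bottle change 28%; week-12 assigned bottle adjusted for both baselines 92% at the 12-week values.
- Learning specific to the opaque bottle: adjusted averaged score 56% down to about 41%.

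The nipple-flow covariate is not in any of these figures. No power is worked for the NCAFS score. The same cancellation applies to it, and whether its stated detectable difference follows from its inputs is a separate question.

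**The case against.** The best defence is that the averaged and assigned-bottle changes are legitimate. Filming both arms with both bottles allows a test of whether 12 weeks of use changes the mother's behaviour whichever bottle she holds. Removing the immediate effect is then the purpose. This stands as statistics: if the effect is learned and carries over, averaging is efficient. But the plan nowhere says that this is the Aim 1 question, and its own wording speaks of the impact of bottle type.

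A second defence is that the intake-tracking device, planned for bottles in both groups, gives other evidence on intake in use. That limits what a null on the filmed feeds could be said to show. It does not settle Aim 1, because Aim 1 ties intake to the feeding observations and the Data Analysis paragraph names no device analysis.

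Third, this is a pilot-feasibility trial. It nevertheless claims 80% power for its hypothesis tests.

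Three stronger readings are tempting and are not supported. A reader might infer that every definition of change loses the effect, but the third reading keeps it in full. A reader might infer from the Table that bottle order is tied to arm, so that pairing visits by number would distort the result. The Table is only an example, its footnote says conditions are counterbalanced, and nothing suggests such pairing. A reader might also infer that the choice of feeds will be made after seeing results. The gap permits that, but the documents do not show it.

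**Conclusion.** The omission is real and should be fixed before analysis. The plan collects four feeds per dyad and analyses one undefined change. Depending on an unstated choice, the same trial has about 5% or about 90% power for the same constant immediate effect of 19.1 mL.

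The cancellation is algebra and needs only that the immediate effect be the same in both arms. The powers rest on the plan's SD and correlations, an assumed 50 per arm and the illustrative 19.1 mL. The proportional case also rests on assumed G, and the averaged-score powers on an assumed same-week correlation. Power for the adjusted week-12 assigned-bottle contrast barely moves with that correlation up to .85.

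The finding is not that the design is unsound or that the averaged analysis is wrong. It is that a null from the averaged or assigned-bottle change would not answer Aim 1 as worded.

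**What to change.** Before analysis, amend the Aim 1 text in four steps:

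1. **Name the feeds.** The primary contrast is week-12 intake, and the NCAFS sensitivity score, in the assigned bottle, opaque versus clear arm.
2. **As a separate precision gain,** use linear regression adjusted for both entry feeds instead of a change score. This step, not the naming of feeds, raises power from about 78% to about 89-92%.
3. **Fix the timing of the nipple-flow covariate.** Take it from the entry feeds. Nipple choice at week 12 is post-randomisation and could be affected by arm.
4. **Add two secondary contrasts,** with the same adjustment: the week-12 clear-bottle feed by arm and the week-12 opaque-bottle feed by arm. The first picks up learning that carries over to the clear bottle but misses learning specific to the opaque bottle. The second picks up opaque-specific learning and is 0 for a purely immediate effect.

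If the sponsor intends the learned effect as primary, the plan should say so and name the feeds to match.

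The cost is wording only, since all four feeds are already planned. The downside is that the proposed primary contrast combines immediate and learned effects, so it must be read with the secondary contrasts.

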- 4) current or past medical conditions that interfere with oral feeding
- 5) history of slow growth or failure to thrive
- 6) weight for length percentile  $<5^{th}$
- 7) diagnosed developmental delay (e.g., Down's syndrome)

While we anticipate this will be rare, any mother reporting that they typically use opaque bottles prior to entry will also be excluded.

Research assistants will provide study information to mothers who respond to our recruitment efforts. Mothers who express interest in participating in our study will be screened by trained research assistants to assess study eligibility (see **Appendix 2** for screening and telephone scripts).

**Procedures to Retain Sample.** To promote retention, we will conduct home-based assessments to minimize participant burden. We will compensate participants a total of \$100 (2 pre-test assessments @ \$20 each, 2 brief intermediate assessments @ \$10 each, and 2 post-test assessments @ \$20 each; see **Table**).

**Randomization.** Mothers will be randomized using a computer-generated randomization scheme. Mothers will be informed of the group to which they are randomized by unblinded research assistants at the end of the Home-Based Pre-Test 2 (see **Table**).

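### Aims 1 and 2 model change by group without the baseline value as a covariate; adding it would cut the variance of the WLZ effect by about 27% if the SDs are equal, at almost no cost

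*Combined protocol and SAP*

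**What the plan says.** The Data Analysis paragraph of Statistical Considerations states: "We will use linear regression to model the change in infant intake and maternal responsiveness (Aim 1) and change in WLZ, skinfolds, waist circumference", with clear versus opaque group as the primary study variable. The only covariate named for the main models is in the infant intake item under Measures, where the investigators "will control for nipple flow rate in all analyses". Infant weight status is listed in Aim 3 as a possible moderator and in Data Analysis as a correlate of the feasibility measures. It is not a term in the main models.

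The Power calculations paragraph treats WLZ as a change score. It claims 80% power "to detect a difference of 0.59 in change of WLZ from baseline to 12-week follow-up". On the inputs it says: "The latter calculation assumes the standard deviation for WLZ is 1.0, and that the correlation between WLZs over 12-weeks for infants is" .45.

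On the baseline data, Assessments and Measures says "we will conduct two assessments (separated by one day) at both study entry and completion", and the infant growth item has weight and length taken at every home-based assessment. Under Randomization: "Mothers will be informed of the group to which they are randomized by unblinded research assistants at the end of the Home-Based Pre-Test 2".

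**The concern.** A change score subtracts the whole baseline value, which amounts to fixing the slope of follow-up on baseline at 1. With equal SDs and a correlation of .45 the best slope is .45, so subtraction over-corrects and adds noise. Regression with baseline as a covariate estimates the slope instead. For WLZ this is a matter of efficiency, not bias.

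The stake is power. Aims 1 and 2 are stated as hypothesis tests, and the sample size is justified as adequate for them. The WLZ calculation only just reaches 80%. The information that would improve it is already needed to form the change score, and it is collected before mothers learn their group.

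**Working it through.** **Inputs from the plan (Power calculations).** WLZ SD 1.0; correlation r = .45; 100 dyads; alpha .05; power 80%; detectable difference 0.59.

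**Assumed.** 1:1 allocation (n = 50 per arm), two-sided test, normal data, and the ratio k of week-12 SD to baseline SD. The plan gives a single SD, which corresponds to k = 1. Nipple flow rate is left out of both models compared.

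**Step 1: reproduce 0.59.**
- Variance of change = 1 + 1 − 2(.45) = 1.10, so SD = 1.0488.
- Detectable difference (normal) = (1.960 + 0.842) × √(1.10 × 2/50) = 0.588. With the t distribution it is 0.594.
- The plan's figure is therefore that of an unadjusted change score.

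**Step 2: add baseline, equal SDs.**
- Residual variance = 1 − .45² = 0.7975.
- Cost of estimating the slope: multiply by 1 + 1/(2n − 4) = 1 + 1/96 = 1.0104, giving 0.8058.
- Reduction = 1 − 0.8058/1.10 = 26.7% (27.5% before the slope cost).

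**Step 3: vary the SD ratio.** Change variance = 1 + k² − 2rk. Adjusted variance = k²(1 − r²), then × 1.0104. Detectable differences and power use the noncentral t, with 98 df (change) and 97 df (adjusted).

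| k | Change variance | Adjusted variance, before slope cost | Variance cut | Detectable difference | Power at 0.59 |
|---|---|---|---|---|---|
| 0.9 | 1.000 | 0.646 | 34.7% | 0.566 → 0.457 | 83.2% → 95.1% |
| 1.0 | 1.100 | 0.7975 | 26.7% | 0.594 → 0.508 | 79.5% → 90.2% |
| 1.1 | 1.220 | 0.965 | 20.1% | 0.625 → 0.559 | 75.3% → 84.1% |
| 1.25 | 1.4375 | 1.246 | 12.4% | 0.678 → 0.635 | 68.3% → 74.0% |
| 1.5 | 1.900 | 1.794 | 4.6% | 0.780 → 0.762 | 56.3% → 58.3% |
| 2.0 | 3.200 | 3.190 | −0.7% | – | 37.2% → 37.0% |

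Break-even is at k of about 1.85. A simulation of 40,000 trials per ratio gave cuts of 26.7%, 12.4%, 4.4% and −0.7% at k = 1, 1.25, 1.5 and 2.

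**Step 4: effect of the entry criterion.** Infants with a "weight for length percentile" below the 5th are excluded, which may narrow the baseline spread. If SD 1.0 and r = .45 describe infants before that exclusion (assumed bivariate normal), the baseline SD becomes 0.900 and the week-12 SD 0.981. Then k = 1.09 and the correlation falls to about .41. The change variance is 1.042, the adjusted variance is still 0.7975, and the cut is 22.7% after slope cost. Power goes from 81.6% to 90.2%. If the inputs already describe enrolled infants, this case does not apply.

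**Step 5: sample size, equal SDs.** For 80% power at 0.59, the change score needs 51 per arm and the adjusted model 38.

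**Aim 1.** The gain is not quantified. The "1.32 point difference in change of NCAFS score from baseline to 12-week follow-up" cannot be reproduced from the stated inputs: the mean change variance is [2(1 − .55) + 2(1 − .40)]/2 = 1.05 in units of SD², and 2.802 × 1.91 × √(1.05 × 2/50) = 1.10 (1.11 with t). The plan also does not say which of the two observations per time point its Aim 1 SDs and correlations describe.

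**The case against.** The strongest objection concerns Aim 1. Each time point has two feeding observations, one with each bottle type. In the example assessment table Pre-Test 1 uses a clear bottle in one group and an opaque bottle in the other, with counterbalancing noted beneath. If the baseline were the pre-test feed with the assigned bottle, it would already contain the acute bottle effect. Suppose, as an assumption, that this effect and the week-12 effect are both −20 mL, and take r = .475 (the mean of .55 and .40). The change score then estimates −20 − (−20) = 0, and the adjusted model estimates −20 − .475 × (−20) = −10.5 mL. Neither recovers −20. This stands: for intake and NCAFS the choice is one of efficiency only if the baseline feed uses the same bottle type in both groups, or averages the two pre-tests. It is a reason to define the baseline, which the planned change score needs equally. It does not affect WLZ.

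Other points carry less weight. The power paragraph confirms an unadjusted change score for WLZ only: the 19.1 mL for intake is as close to a follow-up-only comparison (19.07 with t) as to a change score (19.35 normal, 19.54 with t). Calling group the primary variable does not rule out other terms, but none is named except nipple flow rate, and the gain over a model containing it has not been calculated. Finally, this is a pilot-feasibility study and its WLZ analysis is valid as planned. That limits the severity, but the plan claims adequate power for its hypothesis tests.

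**Conclusion.** The point holds. The main models omit the baseline outcome. On the plan's own WLZ inputs with equal SDs, including it would cut the variance of the group effect by 26.7% and lift power at 0.59 from about 80% to about 90%. The size depends on the SD ratio, which the documents do not give: the cut is 12.4% at 1.25 and 4.6% at 1.5, and a loss of only 0.7% appears at 2.0. The other assumptions are 1:1 allocation, a two-sided test and normal data. A gain in the same direction is expected for intake and NCAFS once their baseline is properly defined, but no figure is claimed. This is a worthwhile improvement to a valid WLZ analysis, not the correction of an error.

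**What to change.** In Data Analysis, add the baseline value of each outcome as a covariate in the existing Aim 1 and Aim 2 regressions. The outcome may remain change from baseline: with baseline in the model, the group coefficient is the same as for the week-12 value.

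State which pre-test value, or the mean of the two, is the baseline. This is needed for WLZ, which is measured at both pre-tests, as well as for intake and NCAFS. For the two feeding outcomes, choose a baseline that has the same bottle type in both groups or averages over both types, and match the week-12 value to it.

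The cost is one sentence for the covariate and one degree of freedom, with no new data. The baseline definition is required for the change score in any case. Make the change before outcome data by group are seen.

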- Maternal responsiveness to infant cues will be objectively assessed by video-coding of all feeding observations. After each visit, three trained coders who are unaware of the experimental conditions and hypotheses of the study will code videos using the NCAFS, a reliable and valid means of observing and rating mother-child interactions during a feeding session. The NCAFS is validated for use with mothers and their 0-1-year-old infants, can be applied to a breast or bottle-feeding episodes, and has been used during both lab- and home-based feeding observations. It contains 76 observable behaviors that are organized into six subscales; for the proposed research, we will

focus the Maternal Sensitivity to Infant Cues subscale. Reliability will be established prior to full coding of all videos. To this end, coders will code 10 common videos, and will double-code 10 additional videos. Inter-coder comparison of the 10 common videos will be used to establish inter-coder reliability. Intra-coder comparison of the 10 double-coded videos will be used to establish intra-coder reliability. Full coding will not commence until a Kappa > 0.80 is reached for all coders. The PI is certified in this coding system and has it previously.

- Maternal feeding style, including responsive and pressuring feeding, will also be subjectively assessed at study entry and completion using the Infant Feeding Style Questionnaire (IFSQ; see Appendix 4), which assesses maternal behaviors (e.g., control) and beliefs (e.g., concern about feeding) related to infant feeding. This scale has been validated in diverse samples of mothers with young infants and the PI has used this measure in previous research.
- Infant growth will be assessed during all home-based assessments by trained research assistants measuring infant weight and height in triplicate using a portable infant scale/infantometer (models 334 and 233; Seca, Hamburg, Germany). To minimize bias, infants will always be weighed and measured while only wearing a clean diaper and prior to the observed feeding. We will use the World Health Organization (WHO) Anthro software version 3.0.1 (http://www.who.int/childgrowth/en/) to calculate age-and sex-specific weight-for-length z-scores (WLZ) based on the WHO growth standards. We will also assess infant adiposity by infant skin-fold thickness and waist circumference using standard protocols.

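### Aim 2 compares entry-to-week-12 change only, so by default it drops dyads without a week-12 visit and leaves the week-2 and week-6 growth data unused; the WLZ contrast shrinks toward zero if slow growers leave the opaque arm more often

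*Combined protocol and SAP*

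**What the plan says.** Under Statistical Considerations, the Data Analysis paragraph gives the Aim 2 method as linear regression of "change in WLZ, skinfolds, waist circumference (Aim 2) by the primary study variable" of clear versus opaque group. The Power calculations paragraph fixes the two time points: the trial is sized "to detect a difference of 0.59 in change of WLZ from baseline to 12-week follow-up". It handles attrition through recruitment: "we conservatively estimate 20% of participants will drop out and 120 mother-infant dyads will be recruited to account for this predicted attrition rate". The same paragraph reports attrition below 10% in the investigators' earlier work.

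Under Assessments and Measures, "Two brief visits will occur at weeks 2 and 6 to assess infant growth and maternal adherence to the intervention". The Measures list adds that "Infant growth will be assessed during all home-based assessments". Aim 2 itself, in the statement of purpose, is a hypothesis about 12-week weight-gain trajectories, and it places weight, length, skinfolds and waist at the start and end of the study.

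The section on potential risks and monitoring says that opaque bottles might lead caregivers to underfeed. It provides for referral of slow-growing infants, and for their removal if participation is judged harmful.

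The document gives no analysis set, missing-data method or sensitivity analysis for Aim 2.

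**The concern.** A change score needs both ends. A dyad with entry, week-2 and week-6 growth but no week-12 visit contributes nothing to the planned regression. Recruiting 120 instead of 100 restores the number analysed, but not the kind of infant who was lost.

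That matters here because the protocol itself describes a route out of the study that depends on growth and is more plausible in one arm. If slow-growing infants leave the opaque arm more often than the clear arm, the opaque completers look heavier than the randomised group would have. The estimated slowing of weight gain is then too small. The early growth that would reveal such loss is scheduled for collection, but no Aim 2 analysis uses it.

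**Working it through.** **1. The plan's own figure.** The stated inputs are: "The latter calculation assumes the standard deviation for WLZ is 1.0"; "the correlation between WLZs over 12-weeks for infants is" .45; 80% power; α = .05 (taken as two-sided); n = 100 (taken as 50 per arm).

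- SD of change = 1.0 × √(2 × (1 − .45)) = 1.049.
- Detectable difference = (1.960 + 0.842) × 1.049 × √(2/50) = 0.588, which reproduces 0.59 (power 80.3%).

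The figure therefore assumes about 100 dyads with both ends measured, which confirms the completer basis. With 120 recruited and 20% lost, 96 remain (48 per arm), and power for 0.59 is 78.7%.

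**2. Bias of the change regression under selective loss.** The documents give no dropout mechanism, dropout timing or interim correlations, so the following are assumptions:

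- true difference −0.59; SD 1; entry to week 12 r = .45 (stated);
- entry to week 6 r = .62; week 6 to week 12 r = .75;
- all loss falls after week 6;
- in the opaque arm only, the log-odds of loss rise by 0.5 or 1.0 for each SD of slower WLZ change to week 6.

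The covariance of the two changes is .75 − .62 − .45 + 1 = 0.68. The SD of change to week 6 is √(2 × .38) = 0.872. So each SD by which completers are shifted on week-6 change moves the week-12 change by 0.68/0.872 = 0.78. Large-sample simulation gives:

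| Loss, opaque / clear | Log-odds 0.5 per SD | Log-odds 1.0 per SD |
|---|---|---|
| 20% / 20% | −0.52 | −0.45 |
| 10% / 10% | −0.55 | −0.52 |
| 30% / 10% | −0.48 | −0.39 |
| 20% / 20%, same selection in both arms | not run | −0.59 |

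A likelihood-type estimate conditioning on entry, week 2 and week 6 returns −0.59 in every row.

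For scale, the standard error with 48 per arm is 1.049 × √(2/48) = 0.214. The 20% / 20% bias of 0.07 to 0.14 is one-third to two-thirds of that. An expected estimate of −0.52 has power of about 68% (0.52/0.214 − 1.96 = 0.47), and −0.45 about 56% (0.45/0.214 − 1.96 = 0.14).

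**3. Extreme bound.** If the 20% of opaque infants with the slowest week-12 change were lost and clear-arm loss were random, the mean shift would be 0.350 SD × 1.049 = 0.37, leaving −0.22. This is a limit, not an expectation.

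**4. Loss driven by unseen week-12 growth.** Correlations were assumed to decay over time to .45 at week 12, with selection from moderate to complete, at 20% loss. Completers give −0.41 to −0.23. Using the interim data recovers only part: −0.51 to −0.39.

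**5. Precision when loss is random.** Variance of unadjusted change is 2 × (1 − .45) = 1.10. Adjusted for entry WLZ it is 1 − .45² = 0.7975. The ratio is 0.725, a cut of about 28% in completers alone. I simulated 60 per arm with 48 completing, taking week-2 correlations as .85 with entry, .78 with week 6 and .55 with week 12. The SD of the estimate was:

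- 0.217 for the planned regression;
- 0.203 for a repeated-measures estimate of change without entry adjustment (variance ratio 0.88);
- 0.177 with entry adjustment (ratio 0.66, a cut of about a third).

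**The case against.** The strongest reply is that nothing in the plan says dropouts are deleted. A reader might infer that it does, but deletion is only what the named model and the completer-based size lead to when no rule is stated. That distinction stands, and the point here is about the default.

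The 20% is a deliberately cautious figure set against earlier attrition below 10%. At 10% loss the bias is 0.04 to 0.07, at most about a third of a standard error. That also stands.

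The direction is not certain. Equal selection in both arms gives no bias. Reversing the selection, so that fast growers leave the opaque arm, would overstate the effect by a similar amount (about −0.59 − 0.07 = −0.66). The protocol also names simple dislike of the bottles, which need not be related to growth. The underfeeding risk and the removal provision make loss of slow growers from the opaque arm foreseeable, not established.

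A reader might further infer that harm would be hidden. The documents do not support that. Aim 3 separately summarises inadequate weight gain and weight loss, reasons for dropout are recorded, and infant growth is monitored with quarterly review by the safety monitor. None of this is confined to completers. It does not, however, repair the between-group WLZ estimate.

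Finally, interim WLZ may not be available. WLZ needs length, Aim 2 lists weight and length only at the start and end, and the brief visits promise growth without naming length. This must be confirmed before the fix can be relied on.

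**Conclusion.** The concern holds as a limitation of the Aim 2 growth contrast. As written, the analysis by default uses only dyads with a week-12 value and ignores scheduled interim growth, which fits poorly with a hypothesis about trajectories. The WLZ difference is biased toward zero only if slow growers are lost more from the opaque arm than from the clear arm. Under the stated assumptions a true −0.59 becomes −0.52 to −0.45 at 20% loss per arm and −0.55 to −0.52 at 10%, and stays at −0.59 if selection is equal.

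These sizes depend on assumed interim correlations, an assumed mechanism, and all loss falling after week 6. It would go too far to say that the effect will be understated, or that a mixed model removes bias whatever the cause of loss. It does so when loss depends on growth already observed. The precision gain needs no differential loss, and most of it comes from using entry WLZ as a covariate. The change is worth making, but for a pilot-feasibility study it is not a fatal flaw.

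**What to change.** For WLZ only:

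- Make the Aim 2 result the week-12 group difference from a repeated-measures mixed model in all randomised dyads with any growth measurement. Use entry (mean of the two pre-tests), week 2, week 6 and week 12 (mean of the two post-tests), with group-by-visit terms and unstructured covariance.
- Use entry WLZ efficiently: either as a covariate with weeks 2, 6 and 12 as outcomes, or as an outcome with entry means constrained equal across arms.
- Confirm in the protocol that length as well as weight is taken at weeks 2 and 6.
- Keep the completers' change regression as a sensitivity analysis, and add one for loss not at random, such as a delta-adjusted analysis. The completers' analysis cannot test that assumption.
- Report loss and its reasons by arm beside the estimate.

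Skinfolds and waist are placed at the start and end in Aim 2, so this model does not help them; state how their missing values are handled.

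The cost is revised analysis wording and a short program in SAS, which the plan already names. No visits are added if length is already measured. The downside is a little more analysis work and reliance on missing-at-random given observed growth. For dyads lost before week 2 there is nothing after entry to recover.
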